**Figure 5 Study GO28141 Dosing Scheme**

BID = twice daily; D = day; QD = once daily.

All patients will be closely monitored for safety and tolerability during all cycles of therapy, at the end-of-study treatment visit, and during the follow-up period. Patients will be assessed for adverse events every 2 weeks during the first 2 cycles, then prior to each subsequent cycle, and as necessary throughout the study.

Tumor response will be evaluated according to RECIST v1.1. Any evaluable and measurable disease must be documented at screening and re-assessed at each subsequent tumor evaluation. Response will be assessed by the investigator at 8-week intervals. At the investigator's discretion, CT/MRI scans may be repeated at any time if PD is suspected.

The NCI Common Terminology Criteria for Adverse Events (CTCAE) v4.0 will be used to characterize the toxicity profile of the study treatments on all patients. ECG monitoring for patients who receive vemurafenib will be conducted in accordance with the vemurafenib IB. Ongoing ECG monitoring is no longer required for patients who continue to receive only cobimetinib/placebo unless clinically indicated. Dermatologic assessment will be performed at the beginning of Cycle 2 ( $\pm 1$  week) and per local

standard of care thereafter. Ophthalmologic examinations and left ventricular function evaluation (echocardiogram or MUGA) are evaluated throughout the study.

Treatment will continue until disease progression, death, unacceptable toxicity, or withdrawal of consent, whichever occurs earliest. Patients on the vemurafenib and placebo treatment arm will be eligible to cross over to the vemurafenib and cobimetinib treatment arm prior to disease progression so long as the patient has not discontinued vemurafenib treatment should the investigator feel that the addition of cobimetinib may benefit the patient and the patient provides informed consent and continues to be followed for survival. Patients who have previously discontinued vemurafenib and who are receiving only placebo may not cross over and should discontinue all study treatment.

### **3.2 END OF STUDY**

The study will end when all patients enrolled have been followed until death, withdrawal of consent, loss to follow-up, or the Sponsor decides to end the trial, whichever occurs first.

Patients may continue on study treatment until the development of progressive disease, unacceptable toxicity, and/or consent withdrawal. Patients who discontinue study treatment for any reason will be followed for SCC according to the risk management plan (see Section 5.1.3), followed for disease progression and followed for survival until death, withdrawal of consent, or they are lost to follow-up. Patients who start subsequent anti-cancer treatment after study treatment discontinuation will still need to be followed for survival and SCC.

### **3.3 RATIONALE FOR STUDY DESIGN**

#### **3.3.1 Rationale for Test Product Dosage/Regimen**

The vemurafenib dose selected was based on clinical efficacy and safety initially observed in Study PLX06-02 (Phase I) at the MTD of 960 mg BID. This was further characterized in Studies NP22657 (Phase II) and NO25026 (Phase III) of vemurafenib in locally advanced unresectable or metastatic melanoma. This dose is the recommended starting dose of vemurafenib.

Study MEK4592g (Phase I) identified the MTD of single-agent cobimetinib to be 60 mg QD on a 21-day on, 7-day off (21/7) schedule and at 100 mg QD on a 14-day on, 14-day off (14/14) schedule. The 21/7 dosing schedule for cobimetinib offers a longer duration of drug exposure and consequently, a more prolonged suppression of MEK compared to the 14/14 schedule. The lower dose of cobimetinib in the 21/7 schedule is also associated with a lower rate of adverse events (including Grade  $\geq 3$  adverse events).

In Study NO25395 (Phase Ib), the combination of vemurafenib and cobimetinib 21/7 was delivered at their respective single-agent MTDs. This dose has cleared the DLT criteria and shown to be tolerable.

Continuous dosing of cobimetinib was not explored in the monotherapy Phase I study (MEK4592g). In Study NO25395, two dose cohorts have been designated to explore continuous dosing cobimetinib with vemurafenib. This dose level may potentially result in poor tolerability at doses that exceed the single-agent MTD of cobimetinib, and result in significant dose reductions that may not adequately suppress the activity of MEK in the tumor cells.

### **3.3.2 Rationale for Patient Population**

The proposed study will enroll treatment-naïve patients with unresectable locally advanced Stage IIIc or metastatic melanoma as defined by the American Joint Committee on Cancer (AJCC) classification v.7. This study will be conducted only in patients whose melanoma harbors the BRAF V600 mutation. This represents the population for which vemurafenib is indicated. The cobas® 4800 BRAF V600 mutation test is the approved companion diagnostic test for vemurafenib and will be used to determine the presence of the BRAF V600 mutation.

Several exclusion criteria were put in place to ensure patient safety going into the study. Patients who are pregnant are not allowed on the study as the effect of vemurafenib and cobimetinib on the developing fetus is not known. Similarly, patients and their partners are required to use of effective contraception.

Given that vemurafenib results in mild QTc prolongation, patients will be required to have a baseline screening ECG and those whose QTc interval is >450 ms or who have congenital long QT syndrome will be excluded.

To mitigate the risk of ophthalmologic adverse events associated with MEKi as a class effect, patients are required to undergo ophthalmologic examination to evaluate risk factor for or findings indicative of neurosensory retinal detachment, CSCR or retinal vein occlusion (RVO) prior to starting study treatment. Patients with such conditions will be excluded.

### **3.3.3 Rationale for Control Group**

Patients on the control arm will receive vemurafenib and placebo. Vemurafenib is the current standard of care for patients with advanced BRAFV600 mutation-positive melanoma, and therefore, would be the standard in which future therapies should be compared against in this patient population.

This will be a placebo-controlled, double-blind study. Use of a placebo control will help to minimize bias in reporting of key assessments of safety, efficacy, and quality of life. After key assessments of these parameters have been assessed, placebo plus vemurafenib patients will be allowed to cross over to active therapy (vemurafenib plus cobimetinib) so long as the patient has not discontinued vemurafenib and provided that the treating physician believes that there will be additional benefit given that the

combination has demonstrated a positive benefit-risk profile over single-agent vemurafenib.

### **3.3.4 Rationale for Pharmacokinetic Assessments**

A sparse sampling strategy will be applied in this study. Samples for PK characterization of cobimetinib and vemurafenib will be collected as outlined in [Appendix 2](#). Samples will be collected on Day 1 and Day 15 of Cycle 1 and Day 15 of Cycle 2. The sampling schedule is designed to enable characterization of vemurafenib and cobimetinib using population PK methodology (pop PK) for characterization following first dose (Day 1) and steady-state (Day 15). In addition, the vemurafenib PK data from Arm A and Arm B will allow evaluation of whether cobimetinib alters vemurafenib pharmacokinetics. The cobimetinib PK data from Arm B will allow comparison to single-agent cobimetinib data to evaluate whether exposures are altered when administered in combination with vemurafenib.

### **3.3.5 Rationale for Collection of DNA for Exploratory Analyses of Pharmacogenetic Polymorphisms**

Genetic variants of drug-metabolizing enzymes and transporters can alter the pharmacokinetics of drugs, affecting their safety and efficacy. For example, patients who carry defective alleles of the gene encoding uridine diphosphate glucuronosyltransferase 1A1 (UGT1A1), which facilitates the metabolism and excretion of SN-38 (the active metabolite of irinotecan), are at higher risk for adverse events associated with the use of standard doses of irinotecan ([O'Dwyer and Catalano 2006](#)). Results from in vitro metabolism studies suggest that cobimetinib is metabolized by cytochrome P450 enzymes CYP3A. A blood sample for DNA isolation will be collected from all patients in this study for potential pharmacogenetic analysis of genes or biomarkers that may affect the pharmacokinetics of vemurafenib and cobimetinib. The decision to analyze the samples will be based on a review of the PK data. For example, if a patient in a given cohort has substantially higher cobimetinib plasma levels than other patients in that cohort, he or she may carry a defective allele of a gene important in the metabolism or transport of cobimetinib. The genotyping efforts would be guided by results from in vitro metabolism studies and by results from ongoing clinical studies with cobimetinib and vemurafenib.

The pharmacogenetic analysis, if needed, will be performed on identifiable DNA samples, because it is necessary to link a patient's PK data with genotype. This analysis may be restricted to the evaluation of genes that may be involved in the pharmacokinetics of cobimetinib and vemurafenib (e.g., drug metabolism, disposition, or elimination genes). Samples may be stored and analyzed up to 5 years after completion of the study, at which time all DNA samples collected for this analysis will be destroyed.

### **3.3.6 Rationale for Biomarker Assessments**

The Sponsor is committed to the collection of biomarker samples in all clinical study protocols. The objective of biomarker profiling is to enable development of treatments specifically targeted for optimal patient benefit. The rationale for the planned biomarker analyses is explained below. However, because the body of knowledge of potential new biomarkers is evolving, the definitive list of analyses may be modified on the basis of new information.

#### **Investigation of Response and Resistance Biomarkers**

This study may explore biomarkers associated with treatment response and resistance, including intrinsic and acquired resistance to BRAF/MEK inhibition in tumor tissues at baseline and at the time of disease progression.

Given the genetic heterogeneity of melanoma tumors, the magnitude of response to combined BRAF/MEK inhibition may be different in certain tumors. To identify mechanisms of resistance, molecular analyses may include assessment of genetic and activation status of the targeted MAPK pathway, potential escape mechanisms such as receptor tyrosine kinases and PI3K/PTEN pathways, and components of the tumor stroma (e.g., tumor infiltrating lymphocytes). These analyses may be conducted at the DNA, RNA, protein, and cell levels. In addition, expression of melanoma prognostic markers and alternative drug targets may be explored. These analyses are essential to identify patients who will benefit the most from the combination therapies and potential cause for resistance, which could help in considering future treatments.

#### **Investigation of biomarkers in plasma samples**

BRAFV600 mutation may be evaluated both in tumor biopsies and in plasma collected during this study. It has been shown that tumor-specific mutations can be identified in plasma of patients. Analysis and correlation of BRAF mutations in plasma and biopsy will help to further evaluate the option of using plasma for the detection of tumor specific mutations.

### **3.3.7 Rationale for Health-related Quality of Life Assessment and Health Economic Assessment**

The HRQL EORTC QLQ-C30 is included to characterize the impact of treatment on patients while receiving and following vemurafenib and cobimetinib exposure. These data should allow for quantification of the health economic impact of these treatments, given the externally validated data generated from the EQ-5D self-reported questionnaire. The collection of this type of data will provide greater insights for both the medical and patient communities to understand patient-reported value and quality of life when exposed to the combination of vemurafenib and cobimetinib treatments.

### **3.4 OUTCOME MEASURES**

#### **3.4.1 Efficacy Outcome Measures**

##### **3.4.1.1 Primary Efficacy Outcome Measure**

The primary outcome measure for this study is as follows:

- PFS, defined as the time from randomization to the first occurrence of disease progression, as determined by the investigator using RECIST v1.1 ([Appendix 3](#)), or death from any cause, whichever comes first.

##### **3.4.1.2 Secondary Efficacy Outcome Measures**

The secondary outcome measures are as follows:

- Overall survival, defined as the time from randomization to death from any cause
- Objective response rate for patients with measurable disease at baseline, defined as complete or partial response as assessed by investigator according to RECIST v1.1
- Duration of response for patients with measurable disease at baseline, defined as the time from first occurrence of a documented objective response until the time of disease progression, as determined by investigator review of tumor assessments using RECIST v1.1, or death from any cause during the study (i.e., within 30 days after the last dose of study treatment)
- PFS as assessed by independent review using RECIST v1.1

#### **3.4.2 Safety Outcome Measures**

Safety outcome measures for this study are as follows:

- Incidence, nature, and severity of adverse events and serious adverse events, graded according to NCI CTCAE v4.0
- Adverse events of special interest: any RVO; any retinal detachment or CSCCR; Grade  $\geq 3$  photosensitivity; Grade  $\geq 2$  LVEF reduction; Grade  $\geq 3$  elevations of AST, ALT, serum bilirubin OR cases of elevated ALT or AST in combination with either an elevated bilirubin or clinical jaundice, as defined in Section 5.3.5.6; Grade  $\geq 3$  QT interval prolongation; and any cutaneous and non-cutaneous primary malignancy, including SCC, KA, BCC, and new primary melanoma.
- Changes in vital signs, ECGs, and clinical laboratory results during the course of study

#### **3.4.3 Pharmacokinetic Outcome Measures**

The following PK parameters will be analyzed using a pop PK approach and will be reported as applicable. Please see Section 6.6 for further details.

- Exposure following first dose and steady-state ( $AUC_{0-24}$ )
- Minimum observed plasma concentration ( $C_{min}$ ; trough concentration)
- Apparent clearance following oral dosing (CL/F)

Exploratory exposure-response analyses for efficacy and safety endpoints, including QTc, will be performed

#### **3.4.4 Patient-Reported Outcome Measures**

The PRO measures for this study are as follows:

- EORTC QLQ-C30
- EuroQol's EQ-5D Questionnaire

The PRO questionnaires (EORTC QLQ-C30 and EQ-5D) were supplied in the local language(s) of each participating country.

#### **3.4.5 Exploratory Outcome Measures**

The exploratory biomarker analyses in tumor tissue may investigate potential intrinsic and acquired resistance mechanisms to MEK and BRAF inhibition. Pre-treatment tumor tissue (i.e., archived material or biopsies collected during screening, prior to initiation of study treatment) and tumor biopsies during treatment (Cycle 2 Day 15) and at the end of study treatment (at the time of PD) will be required.

In order to investigate if chromosomal and molecular genetic aberrations are linked to therapeutic outcome and development of severe adverse events in patients treated with vemurafenib and cobimetinib, DNA may be isolated from a single whole blood collected at baseline as well as tumor tissues.

Additional efficacy exploratory analyses will include PFS rates and OS rates at fixed timepoints (e.g., 3, 6, 9, 12 months, etc.).

### **3.5 MINIMIZATION OF BIAS**

Patients will be randomly assigned to receive vemurafenib and placebo or vemurafenib and cobimetinib through use of an interactive response system (IxRS). Placebo tablets for cobimetinib and packaging configurations will have physical characteristics that will not permit their identification as distinct from those of cobimetinib.

Following the final efficacy analysis and extensive evaluation of safety data, quarterly DSMB review of unblinded safety data will no longer occur. Sponsor personnel will not have access to by-arm efficacy and safety summaries or listings prior to the formal reporting of the primary efficacy results.

Only when knowledge of the investigational product is essential for the safety of the patient, the investigator may unblind a patient's treatment assignment. In such cases, the IxRS system will be used to allow disclosure of an individual patient's treatment assignment to the treating investigator. If the investigator wishes to know the identity of the study drug for any other reason, he or she should contact the Medical Monitor directly (see Section 4.2).

## **4. METHODS AND MATERIALS**

### **4.1 PATIENTS**

To be eligible for Study GO28141, patients must be previously untreated with unresectable locally advanced or metastatic melanoma. Patients must have the BRAFV600 mutation confirmed on their melanoma tumor tissue using the cobas® 4800 BRAF V600 mutation test (see Section 4.5.1.1 and Appendix 10). All patients must meet all of the inclusion and none of the exclusion criteria detailed in Sections 4.1.1 and 4.1.2, respectively.

#### **4.1.1 Inclusion Criteria**

Patients must meet the following criteria for study entry:

##### Disease-Specific Inclusion Criteria:

1. Patients with histologically confirmed melanoma, either unresectable Stage IIIc or Stage IV metastatic melanoma, as defined by AJCC 7th edition (Appendix 8). Unresectability of Stage IIIc disease must have confirmation from a surgical oncologist.
2. Patients must be naïve to treatment for locally advanced unresectable or metastatic disease (i.e., NO prior systemic anti-cancer therapy for advanced disease; Stage IIIc and IV). Prior adjuvant therapy (including immunotherapy, e.g., ipilimumab) is allowed.
3. Documentation of BRAFV600 mutation-positive status in melanoma tumor tissue (archival or newly obtained tumor samples) using the cobas® 4800 BRAF V600 mutation test.
4. Measurable disease per RECIST v1.1 (Appendix 3).
5. ECOG Performance Status of 0 or 1 (Appendix 4).
6. Consent to provide archival tissue (either a paraffin-embedded tissue block or up to 20 unstained slides) for biomarker analyses.
7. Consent to undergo tumor biopsies of accessible lesions on Cycle 2 Day 15 and at progression for biomarker analyses to explore intrinsic and acquired resistance.

##### General Inclusion Criteria:

8. Male or female patient aged  $\geq 18$  years.
9. Able to participate and willing to give written informed consent prior to performance of any study-related procedures and to comply with the study protocol.
10. Life expectancy  $\geq 12$  weeks.
11. Adequate hematologic and end organ function, defined by the following laboratory results obtained within 14 days prior to first dose of study drug treatment:
  - ANC  $\geq 1.5 \times 10^9/L$
  - Platelet count  $\geq 100 \times 10^9/L$

- Hemoglobin  $\geq 9$  g/dL
  - Albumin  $\geq 2.5$  g/dL
  - Bilirubin  $\leq 1.5 \times$  the upper limit of normal (ULN)
  - AST, ALT, and ALP  $\leq 3 \times$  ULN, with the following exceptions:
    - Patients with documented liver metastases: AST and/or ALT  $\leq 5 \times$  ULN
    - Patients with documented liver or bone metastases: ALP  $\leq 5 \times$  ULN
  - Serum creatinine  $\leq 1.5 \times$  ULN or CrCl  $\geq 40$  mL/min on the basis of measured CrCl from a 24-hour urine collection or Cockcroft-Gault glomerular filtration rate estimation:  

$$\frac{(140 - \text{age}) \times (\text{weight in kg}) \times (0.85 \text{ if female})}{72 \times (\text{serum creatinine in mg/dL})}$$
12. Female patients of childbearing potential and male patients with partners of childbearing potential must agree to always use 2 effective forms of contraception during the course of this study and for at least 6 months after completion of study therapy.
- Females of childbearing potential are defined as sexually mature women without prior oophorectomy or hysterectomy who have had menses within the last 12 months.
  - Females are not considered to be of childbearing potential if amenorrheic for  $> 12$  months and follicle-stimulating hormone (FSH) level  $\geq 40$  IU/L.
  - For females who have been amenorrheic for  $\geq 2$  years, the requirement for FSH measurement at screening will be waived.
  - Effective forms of contraception includes surgical sterilization, a reliable barrier method with spermicide, birth control pills, or contraceptive hormone implants. Please note that potential interactions between vemurafenib and hormonal contraceptives may decrease the effectiveness of hormonal contraceptives.
  - Male patients who are surgically sterilized are required to use barrier methods of contraception.
13. Negative serum pregnancy test within 14 days prior to commencement of dosing in women of childbearing potential.
14. Absence of any psychological, familial, sociological, or geographical condition that potentially hampers compliance with the study protocol and follow-up after treatment discontinuation schedule; those conditions should be discussed with the patient before trial entry.

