12. Female patients of childbearing potential and male patients with partners of childbearing potential must agree to always use 2 effective forms of contraception during the course of this study and for at least 6 months after completion of study therapy.
  - Females of childbearing potential are defined as sexually mature women without prior oophorectomy or hysterectomy who have had menses within the last 12 months.
  - Females are not considered to be of childbearing potential if amenorrheic for  $> 12$  months and follicle-stimulating hormone (FSH) level  $\geq 40$  IU/L.
  - For females who have been amenorrheic for  $\geq 2$  years, the requirement for FSH measurement at screening will be waived.
  - Effective forms of contraception include surgical sterilization, a reliable barrier method with spermicide, birth control pills, or contraceptive hormone implants. Please note that potential interactions between vemurafenib and hormonal contraceptives may decrease the effectiveness of hormonal contraceptives.
  - Male patients who are surgically sterilized are required to use barrier methods of contraception.
13. Negative serum pregnancy test within 14 days prior to commencement of dosing in women of childbearing potential
14. Absence of any psychological, familial, sociological, or geographical condition that potentially hampers compliance with the study protocol and follow-up after treatment discontinuation schedule; those conditions should be discussed with the patient before trial entry

Patients who meet any of the following criteria will be excluded from study entry:

Cancer-Related Exclusion Criteria:

1. History of prior RAF or MEK pathway inhibitor treatment
2. Palliative radiotherapy within 14 days prior to the first dose of study treatment
3. Major surgery or traumatic injury within 14 days prior to first dose of study treatment

4. Patients with active malignancy (other than BRAF–mutated melanoma) or a previous malignancy within the past 3 years are excluded; except for patients with resected melanoma, resected basal cell carcinoma (BCC), resected cutaneous squamous cell carcinoma (SCC), resected melanoma in-situ, resected carcinoma in-situ of the cervix, and resected carcinoma in-situ of the breast.
5. History of isolated elevation in prostate-specific antigen in the absence of radiographic evidence of metastatic prostate cancer is allowed.

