#### **4.4 CONCOMITANT TREATMENT**

##### **4.4.1 Permitted Therapy**

Concomitant therapy includes any medication (e.g., prescription drugs, over-the-counter drugs, herbal/homeopathic remedies, nutritional supplements) used by a patient from 7 days prior to Cycle 1 Day 1 through the end-of study treatment visit. All concomitant medications should be reported to the investigator and recorded on the Concomitant Medications electronic Case Report Form (eCRF).

Patients who use oral contraceptives, hormone-replacement therapy, or maintenance therapy should continue their use as outlined in the eligibility criteria. Please note that potential interactions between vemurafenib and hormonal contraceptives may decrease the effectiveness of hormonal contraceptives.

Pain medications may be administered according to local standard practice guidelines while the patient is in the study.

Anti-emetics and anti-diarrheal medications should not be administered prophylactically before initial treatment with study drugs. At the discretion of the investigator, prophylactic anti-emetic and anti-diarrheal medication(s) may be used per standard clinical practice before subsequent doses of study drugs.

Hematopoietic growth factors should not be administered prophylactically before initial treatment with study drugs. Hematopoietic growth factors may be administered according to local guidelines if indicated during the course of the study.

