### ***Teratogenicity and Development Toxicity***

In a dedicated nonclinical embryo-fetal toxicity study, cobimetinib produced fetal toxicity (resorptions and reductions in fetal weight), and teratogenicity (malformations of the great vessels and skull) at similar systemic exposures in rat to those observed in patients administered the 60 mg dose.

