#### **5.4.3 Reporting Requirements for Pregnancies**

##### **5.4.3.1 Pregnancies in Female Patients**

Female patients of childbearing potential will be instructed to immediately inform the investigator if they become pregnant during study treatment or within 6 months after the last dose of study drug. All women of childbearing potential will have a serum pregnancy test at screening.

A Pregnancy Report eCRF should be completed by the investigator immediately (i.e., no more than 24 hours after learning of the pregnancy) and submitted via the EDC system. A pregnancy report will automatically be generated and sent to Roche Safety Risk Management. Pregnancy should not be recorded on the Adverse Event eCRF. The investigator should discontinue study drug and counsel the patient, discussing the risks of the pregnancy and the possible effects on the fetus. Monitoring of the patient should continue until conclusion of the pregnancy.

In the event that the EDC system is unavailable, a Pregnancy Report worksheet and Pregnancy Fax Coversheet should be completed and faxed to Roche Safety Risk Management or its designee within 24 hours after learning of the pregnancy, using the fax numbers provided to investigators (see "Protocol Administrative and Contact Information and List of Investigators").

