## Appendix 1 Schedule of Assessments and Procedures (cont.)

- Start of second cycle after cross over, Day 1  $\pm$  1 week
  - On Day 1 of Cycles 5, 8, and 11 after cross over (every three treatment cycles)  $\pm$  2 weeks
  - On Day 1 of Cycles 15, 19, and 23 after cross over (every four treatment cycles)  $\pm$  2 weeks
  - On Day 1 of Cycles 29, 35, 41, 47 after cross over, etc. (every six treatment cycles)  $\pm$  2 weeks
  - End-of-study-treatment visit
7. Hematology includes hemoglobin, hematocrit, WBC with differential (neutrophils, lymphocyte, monocyte, eosinophil and basophil counts, and other cells), and platelet count. Screening hematology values must be obtained within 14 days of Cycle 1 Day 1. Note: If screening laboratory specimens are collected within 7 days of the Cycle 1, Day 1 visit, they do not have to be repeated at Day 1.
  8. Chemistry includes BUN, creatinine, sodium, potassium, chloride, bicarbonate, phosphorus, magnesium, total calcium, albumin, LDH, and CPK. LFTs include ALT, AST, total bilirubin, ALP, and GGT. Screening chemistry values must be obtained within 14 days of Cycle 1 Day 1. Note: If screening laboratory specimens are collected within 7 days of the Cycle 1, Day 1 visit, they do not have to be repeated at Day 1.
  9. For women of childbearing potential, a serum pregnancy test is required at screening within 14 days prior to Cycle 1 Day 1. Women who have had amenorrhea for  $>$  12 months but  $<$  2 years should have an FSH test at screening for eligibility purposes.
  10. This is performed only during screening. Both blood glucose and lipid panel must be obtained after at least an 8-hour fast. Lipid panel should include total cholesterol, low-density lipoprotein and triglycerides.
  11. All patients must have a screening brain CT or MRI to assess for brain metastasis, and subsequently only as clinically indicated.
  12. The frequency, method, and evaluation criteria for tumor assessments will be determined by the investigator per local clinical practice. Response may be assessed using RECIST v1.1. Assessments should include CT scans of the chest, abdomen and pelvis, with an evaluation of all known or suspected sites of disease, whenever possible. The same radiographic procedure used at screening should be used throughout the study.

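### Inclusion criterion 12 lets a woman meet the two-form contraception rule with two hormonal methods, although the same criterion warns that vemurafenib may weaken hormonal methods

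*Protocol*

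**What the plan says.** Criterion 12 in Section 4.1.1 requires female patients of childbearing potential, and male patients with partners of childbearing potential, to "always use 2 effective forms of contraception during the course of this study and for at least 6 months after completion of study therapy". It names the acceptable forms: "Effective forms of contraception includes surgical sterilization, a reliable barrier method with spermicide, birth control pills, or contraceptive hormone implants". The synopsis gives the same four: "Effective forms of contraception include surgical sterilization, a reliable barrier method with spermicide, birth control pills, or contraceptive hormone implants". In both places the next sentence is a warning: "Please note that potential interactions between vemurafenib and hormonal contraceptives may decrease the effectiveness of hormonal contraceptives".

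Section 4.4.1 (Permitted Therapy) returns to the subject: "Patients who use oral contraceptives, hormone-replacement therapy, or maintenance therapy should continue their use as outlined in the eligibility criteria". It then repeats the warning and adds no requirement.

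Two other statements bear on the consequences. Section 5.1.2.2 reports that cobimetinib caused "teratogenicity (malformations of the great vessels and skull) at similar systemic exposures in rat to those observed in patients administered the 60 mg dose". On testing, Section 5.4.3.1 says "All women of childbearing potential will have a serum pregnancy test at screening", and footnote 9 of Appendix 1 says "For women of childbearing potential, a serum pregnancy test is required at screening within 14 days prior to Cycle 1 Day 1". The schedule shows no later pregnancy test.

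**The concern.** In a two-form rule the second method is there to work when the first fails. That backup is weakened if one cause can impair both. Criterion 12 identifies such a cause, the interaction between vemurafenib and hormonal contraceptives, but its list contains two hormonal forms and the warning is advisory only. As written, a woman on a pill plus an implant satisfies the criterion while both her methods fall under its warning.

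What is at stake is fetal exposure to a drug that was teratogenic in rats at exposures like those in patients. Because pregnancy testing is scheduled only at screening, prevention after entry rests on the contraception rule. Efficacy and safety results are not at stake.

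**Working it through.** **1. Does the rule admit an all-hormonal pair?**

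- Forms required: 2 (criterion 12).
- Forms named: 4, namely sterilization, barrier with spermicide, pills and hormone implants. The last two are hormonal.
- Pairs among the four: C(4,2) = 6. Wholly hormonal pairs: C(2,2) = 1, the pill plus implant.

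This counts combinations, not patients. The list is introduced with a form of the verb include, so it may not be closed.

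**2. Does any other part of the protocol exclude that pair?**

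- Section 3.3.2 asks only for effective contraception.
- Section 4.4.1 sends users of oral contraceptives back to the eligibility criteria, so the reference is circular.
- Section 4.4.4 calls vemurafenib a CYP3A4 inducer, and Appendix 11 says exposure to the CYP3A4 substrates it lists may fall. Neither mentions contraceptives or asks for a non-hormonal form.
- Section 5.4.3.1 covers reporting and management of pregnancy.
- Footnote 2 of Appendix 1 (crossover) does not mention contraception.
- The only compulsory barrier rule in criterion 12 is for surgically sterilized male patients.

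Nothing closes the gap.

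**3. For how long would a non-hormonal form be needed?**

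The warning concerns vemurafenib, so the relevant period is treatment with vemurafenib plus the time the drug takes to clear. The protocol states no half-life for vemurafenib. Section 1.2.1 allows two estimates, both assuming one-compartment kinetics and taking five half-lives as washout.

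*From accumulation.* The median accumulation ratio is 7.36 for twice-daily dosing (12-hour interval):

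- k = −ln(1 − 1/7.36)/12 = 0.0122 per hour
- half-life = 0.693/0.0122 = 57 h
- 5 × 57 h = 285 h, or 11.9 days

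*From clearance.* AUC over 12 hours is 734 µg/mL·h and apparent volume is 91 L. A dose of 960 mg twice daily is assumed for the pooled data:

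- CL/F = 960/734 = 1.31 L/h
- half-life = 0.693 × 91/1.31 = 48 h
- 5 × 48 h = 240 h, or 10.0 days

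The two routes agree on about 10 to 12 days for a typical patient. Section 1.2.1 reports high variability between patients, so some will take longer. Any further lag before the interaction itself wears off is not given in the documents and is not counted.

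**4. Does cobimetinib alone carry the same weakness?**

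The documents do not show it. The warning names vemurafenib only. Section 4.4.4 reports, as preliminary, no effect of cobimetinib on CYP3A: the midazolam AUC ratio was 1.06 (95% CI 0.84 to 1.32).

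**The case against.** The strongest reply is that the risk is disclosed where it matters. The warning stands directly beside the list and is repeated in Section 4.4.1. The rule asks for two effective forms and tells the investigator why hormonal forms may be less so. Leaving the pairing to an informed investigator is a drafting choice, and the protocol states nothing false. Women are also told to report pregnancy at once, and study treatment stops if it occurs. This is fair and limits the weight of the point. It does not remove it: a warning without a requirement still lets the pair through, and reporting shortens exposure but does not prevent conception.

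A second reply is timing. Section 1.4.4 shows all 495 patients (247 + 248) enrolled and the final survival analysis done, so the edit screens nobody new. It matters only for women still on vemurafenib or within its washout, a number the documents do not give. That stands.

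A reader might also infer more than the documents support:

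- *That a non-hormonal form is needed for the whole contraception period, including six months after therapy.* The washout of 10 to 12 days does not support that length.
- *That it is needed while cobimetinib continues alone.* Table 10 allows this after vemurafenib stops. It is a reason to continue contraception, which criterion 12 already requires. It is not evidence that hormonal methods are weakened, given the CYP3A result in Section 4.4.4.
- *That crossover needs its own clause.* Sections 3.1 and 3.3.3 open crossover only to patients who have not discontinued vemurafenib. Those women are already under criterion 12 with the same interaction.
- *That the rule for partners of male patients has the same defect.* Those partners do not take vemurafenib as study treatment.

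**Conclusion.** The point holds as a minor patient-safety wording gap. Criterion 12 accepts two hormonal methods as the two required forms, although it warns about that class of method, and no other text in the protocol prevents it. The correction is worth making because it is cheap and the possible harm is fetal exposure.

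The practical size is unknown and probably small. The documents do not quantify the interaction, and they give neither the number of women of childbearing potential on treatment nor how many use a pill plus an implant. The conclusion rests on the protocol text alone. The consent form is not at hand and may contain further advice. The washout figure rests on one-compartment kinetics and the assumed 960 mg dose.

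**What to change.** Add one sentence to criterion 12 in the synopsis and in Section 4.1.1, with a cross-reference in Section 4.4.1:

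*For female patients of childbearing potential, at least one of the two forms must be non-hormonal (e.g., a barrier method with spermicide or surgical sterilization) while taking vemurafenib and through its washout after the last dose.*

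Keep the examples open-ended so that other non-hormonal methods are not excluded by accident. The sponsor should state the washout length, starting from the 10 to 12 days above and allowing for any lag in the interaction that it knows of. It may prefer to apply the requirement for the whole contraception period for simplicity, but that would be a choice of convenience. Leave the rule for partners of male patients and the crossover footnote unchanged.

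The cost is one sentence in two places and a cross-reference in a third. A woman relying only on hormonal methods would have to add or replace one.
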